7.1.3. Product change

Every time the subject changes the full product or baseplate (2-piece users) they will use the clinical trial app to complete a questionnaire about skin condition, reason for change, use of accessories and ballooning. In addition, they will be asked to take photos of the peristomal skin and the back side of the removed product (leakage).

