11.2. Sample size

The itching score is given at each baseplate change and the max of these scores per week at steady state is the primary endpoint. The max score is only calculated if there are measurement for more than four days within a week. For each subject approximately three measurements will be available for each test period.

The sample size calculation is based on a simplified linear mixed model with only 1-pc users and no period effect (corresponding to the design from CP300). The model includes a fixed effect of product (comparator and test product), a random effect of subject and a random interaction effect of product and subject.

Based on data from CP300 it is assumed that the total standard deviation of the primary endpoint is 1.82 and that the total variation 1.82² is divided so that:

- a random effect of subject accounts for 68% of the total variation
- a random interaction effect of product and subject accounts for 0%
- and the residual accounts for 32% of the total variation

In table 1 the needed sample size is calculated by simulation for varying values of the true difference between comparator and test product regarding mean max itching score per week and for different values of the power to demonstrate that the difference is significantly different from 0.

Table 4: Subjects needed for comparing mean max itching score between two products

True difference	Reduction in mean if the mean for the comparator is 2.2 as for [REDACTED] in CP300	Power		
		0.8	0.85	0.9
0.6	27%	46	>46	>46
0.7	32%	35	40	45
0.8	36%	30	32	36

Based on the numbers in the table, 40 subjects should test each product to ensure a power of 85%, if the true difference between the comparator product and a test product is 0.7 (corresponding to a 32% reduction if the mean for the comparator is 2.2 as in CP300). This will be enough when comparing the two products. 1-pc and 2-pc users will be evaluated separately (in a combined model). As there are no previous data for 2-pc users the sample size calculations for 1-pc users is assumed to cover 2-pc users as well. To take a potential drop-out (20%) into account it is recommended to include a total of 48 1-pc and 48 2-pc users, resulting in a total of 96 subjects.

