12.1. Data Collection in the clinical investigation

Data will be collected through an electronic data capturing system on the eCRF, a secure, internet-based case report form. This system will be used to record all subject information collected in the investigation for secure data tracking and centralised data monitoring ("remote monitoring") done by monitors, as defined in the monitoring plan.

The data management system is delivered by Medidata Solutions and is named Rave. Current version number is version 2018 2.2. The system is designed for electronic data capture, and it is compliant with the requirements of 21 CFR part 11. It is a validated data management system allowing only qualified and trained personnel to enter the system. The system has full audit trail and electronic signature.

Principal Investigator, or delegate, at the clinical site will perform primary data collection directly into the eCRF or drawn from source-document (medical records) reviews. These data will be uploaded to the data base on a continuously basis. The electronic CRF will be completed on a continuous basis starting from the point of enrolling the subject to final follow up. The sponsor, or delegate, will provide clinical monitoring, including review of eCRF with verification to the source documentation, as defined in the monitoring plan.

The subject will receive a smartphone with the Clinical Trial App installed. The app is developed on behalf of Coloplast A/S by the app development company [REDACTED]. This Clinical Trial App is used during the investigation every time the subject makes a product (1pc) or baseplate (2pc) change.

All data must be recorded in the eCRF during the visit or immediately after.

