22.1. Appendix 1 - Endpoints

The column "Description of endpoints" includes endpoints where the corresponding analysis is described in the statistical analysis section. The column "Measurement" includes measurements that will be summarized and/or listed. The column "Derived from" describes the questions in the eCRF/APP or the method used as basis for the endpoint or measurement. The three last weeks in each test period is in the table referred to as "steady state".

[figure not shown]
Type of endpoint	Group of endpoint	Description of measurement	Derived from	Origin	Assessed by	V1	V2	V3	Calls	Product change
Primary	Itching	1. Max itching score within a week at steady state	The individual itching score per baseplate on a scale from 0-10 (see question below)	Skin condition	Sponsor					X
	Secondary	Max itching score per baseplate change (0-10) at steady state	How much of the time have you experienced any itching around your stoma since you last changed your product? (tick one box only)	Skin condition	Subject					X
		Frequency of itching per baseplate change at steady state	
 None of the time A little of the time Some of the time A lot of the time All of the time 							
			Please rate how itchy the skin around your stoma has been at its worst since you last changed your product (tick one box only) (Scale from 1-10, very mild itch - worst itch possible)							
		2. Frequency of itching in	How often have you experienced itchy skin around your stoma in the past 14 days?	Subject	Subject (Visit CRF)					X

CONFIDENTIAL

Type of endpoint	Group of endpoint	Description of Measurement	Derived from	Origin	Assessed by	V1	V2	V3	Calls	Product change
			
 None of the time A little of the time Some of the time A lot of the time All of the time 							
Pain	3. Max pain score within a week at steady state	The individual pain score per baseplate on a scale from 0-10 (see question below)	
Skin condition
 	
Sponsor
						

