22.4. Appendix 4 – Baseline data

Baseline data – registered at the inclusion visit (V1) by Principal Investigator, or a delegate.

- Date of Informed Consent (date)
- Date of visit (date)
- Check of inclusion criteria
- Check of exclusion criteria
- Subject number (number - automatically generated in eCRF)
- Randomisation number (number - automatically generated in eCRF)
- Name/type of randomised product (list of investigational products)

Demographic

- Date of birth (date)
- Gender (male/female)
- Height (number - cm)
- Weight (number – kg)

Stoma

- Age of stoma (month (if available) and year when created)
- Type of stoma (ileostomy/colostomy)
- Cause of the stoma (Crohn's disease/Colitis ulcerosa/ Cancer/ Other)
- Size of the stoma (diameter on widest place and height)
- Shape of the stoma/intestine (round/oval/irregular)

Current product

- What is your Current product (brand, product name, item number, size, product type (1-piece/2-piece))?
- Are you used to cutting the baseplate? (Yes/No)
 - If yes, how much is cut off from the baseplate (*min and max cut in mm?*)
- Which stoma accessories do you normally use? (*You may tick more than one box*) (None, Adhesive remover, Paste, Rings, stoma tape, stoma belt, Hernia belt, Stoma powder, Barrier lotion, barrier cream, barrier spray or barrier wipes, Cleansing wipes/cleansing spray, Odour remover, Other accessories)
 - If 'other accessories', please specify
- On average, how often do you normally change your product (1pc)/baseplate (2pc)? (Once or more per day, Every second day, Every third day, Every fourth day, Every fifth day, Every sixth day, Once a week or less frequent)

CONFIDENTIAL

Peristomal skin area

- How often do you experience peristomal skin complications (itching, burning, red or discoloured skin, pain, bleeding, moist or broken skin)? (Daily, Every 2-3 days, every 4-6 days, Once a week, Once every second week, More rarely)
- Which peristomal skin complication/symptom do you experience most often? (itching, burning, red/discoloured skin, pain, bleeding, moist or broken skin)
- Body profile with body check tool
- How many times in the last year have you had a peristomal skin complication, where you had to seek consultation and/or treatment from a health care professional?

Leakage/output

- What is the frequency of your output? (All the time (continuous)/with regular intervals/with irregular intervals)
- Bristol scale score
- Do you experience ballooning (air in the bag)? (Yes/no)

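### The itching items behind the primary endpoint look back to the last change of 'product' for every user, although the score is per baseplate, so the recall window for 2-piece users is ambiguous

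*Combined protocol and SAP*

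**What the plan says.** Appendix 1 (Endpoints) derives endpoint 1 from a baseplate-level score: "The individual itching score per baseplate on a scale from 0-10 (see question below". Section 11.2 (Sample size) agrees on the unit: "The itching score is given at each baseplate change and the max of these scores per week at steady state is the primary endpoint".

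Two app items feed that score. The frequency item asks "How much of the time have you experienced any itching around your stoma since you last changed your product". The severity item that follows asks for the worst itch "since you last changed your product (tick one box only) (Scale from 1-10, very mild itch - worst itch possible". The severity scale starts at 1 and the endpoint scale at 0, so the zero presumably comes from a 'none' answer to the frequency item. Both items therefore matter. The pain, burning, overall discomfort and ability-to-move items in Appendix 1 use the same look-back. No 2-piece version of any of them is shown.

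Other parts of the plan separate the two terms. Section 7.1.3 (Product change) says: "Every time the subject changes the full product or baseplate (2-piece users) they will use the clinical trial app to complete a questionnaire". Section 12.1 says the app is used "every time the subject makes a product (1pc) or baseplate (2pc) change". Sections 4.1 and 7.3 and inclusion criterion 13 make the same distinction. So does a baseline question in Appendix 4: "how often do you normally change your product (1pc)/baseplate (2pc".

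**The concern.** On a 2-piece system the bag can be changed while the baseplate stays on. A 2-piece user who does this, and who takes *product* to mean the bag, would answer only for the time since the last bag change. The questionnaire is not completed at bag-only changes, so the earlier part of that baseplate's wear would go unscored and could not be recovered later.

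Three things would be affected:

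- **Meaning of the score.** A maximum over part of the wear is not the per-baseplate score that the endpoint defines.
- **The 2-piece product difference.** 2-piece users are 48 of the 96 subjects, and section 11.2 evaluates them separately within the combined model. Noise, and possibly some dilution, would enter that estimate.
- **The comparison between product types.** Section 11.1 plans to estimate differences between 1-piece and 2-piece users of the same product. If 1-piece scores cover full wear and some 2-piece scores do not, part of that contrast is an artefact of wording.

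**Working it through.** **Step 1: the wording, side by side.**

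| Element | Term used | Place |
|---|---|---|
| Unit of the primary score | baseplate | Appendix 1, endpoint 1; section 11.2 |
| Event that triggers the app | product (1-piece) or baseplate (2-piece) | sections 4.1, 7.1.3, 7.3, 12.1 |
| Baseline question on change frequency | product (1-piece) or baseplate (2-piece) | Appendix 4 |
| Look-back of the itch frequency and severity items | product, all users | Appendix 1 |
| Look-back of the pain, burning, discomfort and mobility items | product, all users | Appendix 1 |

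The items are the only one of these elements that gives a 2-piece user no pointer to the baseplate. Section 7.1.1 says subjects are shown how to complete the questionnaires, but not how *product* is explained to them.

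**Step 2: reproduce the plan's sample size.** Inputs from sections 11.2 and 11.3: total SD 1.82, residual share 32%, product-by-subject share 0%, difference 0.7, 5% level (taken as two-sided).

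- Residual variance = 0.32 × 1.82² = 1.060.
- Standard error of the within-subject difference, 40 subjects, one weekly maximum per product = √(2 × 1.060 / 40) = 0.230.
- Noncentrality = 0.7 / 0.230 = 3.04. Power = 84.3% (t, 39 df) or 86.0% (normal), against the stated 85%.
- Required n = 41 (t) or 39 (normal), against the stated 40.

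With the roughly three weekly maxima per period that section 11.2 describes, the standard error is √(2 × 1.060 / (3 × 40)) = 0.133 and power at 40 is about 99.9%. The stated 40 therefore reproduces only with one maximum per product.

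**Step 3: an illustration of size.** Section 5.1.6 expects two baseplates every three days, so average wear is 72 / 2 = 36 hours. Everything else here is assumed: one bag change halfway, so half the wear is unscored; itch varying independently between 12-hour blocks with SD 0.5 to 1; an effect proportional to the comparator mean of 2.2; and a fraction f of 2-piece users misreading the item.

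- Blocks per week: 14 in full, 7 if half are unscored. Expected maximum of 14 normal values = 1.703 SD; of 7 = 1.352 SD.
- Drop in the weekly maximum for a misreader: 0.351 × SD = 0.18 (SD 0.5) to 0.35 (SD 1).
- Observed difference = 0.7 × (1 − f × drop / 2.2).

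| f | Difference | Power, n = 40, one maximum | Power, n = 40, three maxima |
|---|---|---|---|
| 0 | 0.70 | 84.3% | 99.9% |
| 1/3 | 0.66 to 0.68 | 80.2% to 82.3% | 99.8% to 99.9% |
| 1 | 0.59 to 0.64 | 70.3% to 77.9% | 99.1% to 99.7% |

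**Step 4: sensitivity.** If itch persists (correlation 0.8 between neighbouring blocks, also an assumption), the drop at SD 1 is about 0.21 instead of 0.35. The difference when all misread is then 0.7 × (1 − 0.21 / 2.2) = 0.63, with one-maximum power of about 76%. If the product effect is additive rather than proportional, the expected difference stays at 0.70 and only precision suffers.

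**The case against.** The strongest reply is that context settles the meaning. A 2-piece user sees these items only after removing a baseplate, so the natural reading is the time since the last such removal. Sections 4.1 and 7.1.3 themselves call the removed, photographed item the *product*, section 7.1.3 covers baseplate changes under a product-change heading, and the app's question on the reason for changing offers baseplate detachment as an answer. This stands: the intended reading is the likely one. It does not close the gap, because the item never states the start of the window and the reasons for change also include bag problems such as ballooning.

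A second reply is that harm needs both a bag-only change and a misreading, and the documents give a rate for neither. This also stands. So does the criticism that the illustration is close to a worst case. It ignores persistence of itch, and it treats itch as equally likely throughout wear. Itching and pain are listed reasons for changing; where they trigger the change, the worst itch falls late in the wear, inside even a bag-based window.

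Two stronger readings are tempting. A reader might infer that the trial loses material power. That rests on one weekly maximum per product and a proportional effect; with about three maxima the illustrated loss is negligible. A reader might also infer bias toward one product, since section 4.4.3 allows that the new baseplate could change wear time, and so the unscored share. The documents show no such difference in bag-change patterns, and each subject answers the same items under both products, so no direction can be claimed.

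**Conclusion.** The point holds as a wording ambiguity in the items that generate the primary endpoint and several secondary ones. For 2-piece users the start of the recall window is not stated, although the plan has suitable wording elsewhere. The plausible consequences are extra measurement error, possible dilution of the 2-piece product difference, and a less clean 1-piece versus 2-piece comparison.

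The size cannot be estimated from the documents. The figures above show what would follow under stated assumptions and are not expected effects. The case for acting rests on what the score means and on comparability between product types, not on lost power. It is a cheap improvement, not a flaw that threatens the trial.

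**What to change.** Before the first subject, word every app item that has this look-back with the split already used in Appendix 4, so that the window runs from the last change of product (1-piece) or baseplate (2-piece). Alternatively, show 2-piece users only *baseplate*. Apply this to the itching, pain, burning, discomfort and mobility items, and amend Appendix 1 to match.

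The cost is an edit to the app text and its translations. If the app shows different text by product type, the wording differs slightly between strata and should be noted where the two types are compared; one combined phrase for everyone avoids that. A sentence in the app training at visit 1 would help, but it should support the item text, not replace it. Scores collected before a change cannot be corrected afterwards, so it belongs before the January 2020 start of enrolment.

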4.3. Discussion of clinical investigation design

The open-label, randomised, controlled, comparative, cross-over design was selected for CP288 based on the following advantages:

Randomised:

- The randomisation ensures that the study effect, including selection bias and confounding covariates are adjusted for.

Cross-over:

- The influence of confounding covariates is reduced because each cross-over subject serve as his or her own control.
- Cross over design allows us to assess user preference as all users will try both the new non-CE marked product and one of five CE marked products
- Subjects are their own control and fewer subjects need to be included, even though the test period is longer.
- Requires fewer subjects than parallel designs.

Open label:

- The investigation is not blinded because the Coloplast investigational product and comparators are visibly different from each other.

Enrolment period:

- The duration of the test periods ($42^{\pm 3}$ days) and number of visits should be adequate to assess data on the wear time, leakage pattern, and skin condition of the subjects. The investigational products are tested for $42^{\pm 3}$ days to ensure that the skin will have time to adjust to new conditions, reach a steady state, and for the subjects to test an adequate number of products to give a thorough evaluation of the products.

To account for a possible carry-over effect the steady state period of the treatment period begins after three weeks of product use as it is anticipated that the skin has adapted to the new product after three weeks. The statistical analysis will evaluate if there are signs of a carry-over effect and take that into consideration when presenting the results.

CONFIDENTIAL

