4.6. Blinding

No blinding will be used in this investigation, as it is not possible to blind the products due to visible differences.

CONFIDENTIAL

5. Investigational products

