11.4. Pass/fail criteria

The purpose of the investigation is fulfilled if a significant difference in one of the skin endpoints is estimated.

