		Max overall physical discomfort per baseplate change (0-10) at steady state	How would you rate your overall physical discomfort from skin around your stoma since you last changed your product? (tick one box only) (11-point scale from No discomfort to A lot of discomfort)	Skin condition	Subject					
Overall ability to move around	11.	Max overall ability to move around score within a week at steady state	The individual overall ability to move around score per baseplate on a scale from 0-10 (see question below)	Skin condition	Sponsor					X
		Max overall ability to move around per baseplate change (0-10) at steady state	How much have skin complications around your stoma caused you difficulty in your overall ability to move around since you last changed your product? For example,	Skin condition	Subject					X

CONFIDENTIAL

Type of endpoint	Group of endpoint	Description of Measurement	Derived from	Origin	Assessed by	V1	V2	V3	Calls	Product change
Overall ability to stick the stoma bag adhesive to your skin	12. Max overall ability to stick the stoma bag adhesive to your skin score within a week at steady state	The individual Overall ability to move around score per baseplate on a scale from 0-10 (see question below)	Skin condition	Sponsor						
Discoloration (DET score also includes a discoloration endpoint	13. Discoloration area score (cm^2) per baseplate change at steady state	Max overall ability to stick the stoma bag adhesive to your skin change (0-10) score per baseplate at steady state	Skin condition	Subject						
Intensity	14. Intensity score (cm^2) in the inner zone per baseplate change at steady state	Based on discoloration area in different zones close to the stoma estimated by [REDACTED] from photos of the skin	Skin condition (photos of skin)	Sponsor, from photos taken by subject						
		Based on area with a given intensity estimated by [REDACTED] from photos of the skin	Skin condition (photos of skin)	Sponsor, from photos taken by subjects						

CONFIDENTIAL

CONFIDENTIAL

Type of endpoint	Group of endpoint	Description of endpoint	Measurement	Derived from	Origin	Assessed by	V1	V2	V3	Calls	Product change
Explorative endpoints		end of treatment									

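### The no-blinding rule in section 4.6 does not justify unmasked handling of the skin photos behind endpoints 13 and 14; coding the photos would be a cheap improvement

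*Combined protocol and SAP*

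**What the plan says.** - **Blinding.** Section 4.6: "No blinding will be used in this investigation, as it is not possible to blind the products due to visible differences". Section 4.3 gives the same single reason: "The investigation is not blinded because the Coloplast investigational product and comparators are visibly different from each other". Neither section makes an exception for reading or processing images.
- **Assessor.** Appendix 1 lists endpoint 13 as "Sponsor, from photos taken by subject" and endpoint 14 as "Sponsor, from photos taken by subjects".
- **Derivation.** Endpoint 13 is "Based on discoloration area in different zones close to the stoma estimated by [REDACTED] from photos of the skin". Endpoint 14 is "Based on area with a given intensity estimated by [REDACTED] from photos of the skin". Both are reported in cm².
- **Photos.** Under section 7.1.3 the subject photographs two things at each change: the skin around the stoma, and the adhesive side of the product just taken off.
- **Analysis.** In section 11.1 each skin photo is an observation for these two endpoints. The same section lets individual data points judged invalid be left out, provided this is documented. It does not say that the judgement is made without knowledge of product. No multiplicity adjustment is planned.
- **Success.** Section 11.4: "The purpose of the investigation is fulfilled if a significant difference in one of the skin endpoints is estimated".

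**The concern.** The reason given for an open-label trial is sound for the subject, the site staff and the photo of the used baseplate, because each of them sees the product. It does not automatically extend to a photo of skin after the product has come off, handled away from the subject.

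Most other skin endpoints are self-reports by subjects who know what they are wearing, or DET items completed by investigators who also know. The photo measures are the ones for which part of the chain could be masked. Each is a skin endpoint, so a significant result on either would fulfil the purpose of the investigation under section 11.4. If someone who knows the product decides which images are usable, where a zone lies or which values are invalid, that knowledge can reach a result that counts as success.

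**Working it through.** **1. Does the stated reason cover the skin photos?**

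| Item | Visible product difference in view? | Reason in 4.6 applies? |
|---|---|---|
| Subject wearing the product | Yes | Yes |
| Investigator at visits | Yes | Yes |
| Photo of the adhesive side (leakage endpoints) | Yes | Yes |
| Photo of peristomal skin (endpoints 13 and 14) | Product not in view, unless it leaves a trace | Not by itself |

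The last row rests on an inference: skin under a baseplate can be photographed only once the baseplate is off.

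**2. Who or what makes the estimate?** The estimator is redacted for both endpoints. The assessor label does not settle it, because Appendix 1 also lists the sponsor for maximum itching, pain and burning scores, which are maxima of values entered by the subject, and for median wear time, which is a calculation.

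**3. Where could judgement enter even if measurement is automated?** Accepting or rejecting images, marking zones if done by hand, and omitting data points under section 11.1. The readable text provides no masking for any of these, and section 4.6 says that none will be used.

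**4. How sensitive is the conclusion to a shift?** The plan states no figure on this point, so there is none to reproduce. The documents give no SD or reading error for the photo scores, so what follows is an illustration under assumptions.

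- Number of subjects: 40 per product type, 80 in total (section 11.2, before the drop-out allowance).
- Level: 5% (section 11.3). Sidedness is not stated; two-sided is assumed.
- Assumed: no true difference, and a systematic shift of *b* SDs of the within-subject difference in one direction.
- Simplification: a paired normal test instead of the planned mixed model on individual photos.

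Rejection probability: P = Φ(b√n − 1.96) + Φ(−b√n − 1.96)

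| Assumed b | b√40 | P, n = 40 | b√80 | P, n = 80 |
|---|---|---|---|---|
| 0 | 0 | 5.0% | 0 | 5.0% |
| 0.1 | 0.63 | 9.7% | 0.89 | 14.5% |
| 0.2 | 1.26 | 24.4% | 1.79 | 43.2% |

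The n = 40 column matches the intention in section 11.2 to evaluate 1-piece and 2-piece users separately. The n = 80 column applies if they are pooled.

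**The case against.** A reader might infer that sponsor staff score the skin photos by eye while knowing the product. The documents do not support this. The estimator is redacted, the sponsor label is also used for purely derived variables, and an area in cm² suggests image measurement more than grading. Volume points the same way. At the change rates in section 5.1.6, three steady-state weeks in each of two periods give 48 × 21 × 2 = 2,016 photos from 1-piece users and 48 × 14 × 2 = 1,344 from 2-piece users, about 3,360 in all. If the estimate is automated, bias in the measurement may be close to nil. Redacted text could also describe how the photos are handled.

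Four further objections are fair. A product may leave an imprint or residue on the skin, so coding might not mask fully. Unblinded subjects take the photos, so timing, cleaning, lighting and missed photos stay open to influence whatever happens later. The shifts of 0.1 and 0.2 SD have no source in the documents. These are two secondary endpoints in a study that calls itself exploratory.

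All of this stands, and it limits the point to the manual steps. It does not remove the point. Section 4.6 is an explicit rule without exceptions, so this is more than a missing detail. If masked handling is described in redacted text, section 4.6 contradicts it and still needs rewording. Imperfect masking of image acceptance is better than none.

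**Conclusion.** The point holds in a limited form. The visible difference between products is no reason in itself to leave skin-photo handling unmasked, and the plan applies its no-blinding rule there all the same. What is exposed is any manual step for endpoints 13 and 14: image acceptance or rejection, zone marking, and omission of data points. Biased measurement is not shown, and neither is manual scoring by the sponsor.

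The size of any bias cannot be derived from the documents. The illustrative rates show only that a modest one-directional shift would matter: about 10% to 24% with 40 subjects and 14.5% to 43% with 80, for assumed shifts of 0.1 to 0.2 SD. The point carries weight because either endpoint alone can meet the criterion in section 11.4. It does not touch the primary endpoint, which the subject reports, or the leakage endpoints, for which the stated reason is valid.

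**What to change.** A cheap improvement:

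1. Reword section 4.6 so that the absence of blinding is limited to subjects and site staff.
2. Give the skin photos random codes with product, period and date removed, and keep them apart from the adhesive-side photos.
3. Carry out image acceptance, any manual marking and any exclusion of photo data points under section 11.1 on the coded set.
4. Lock the values, then link them to product.
5. If estimation is fully automated, say so in Appendix 1 and mask only the manual steps.

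The cost is a small data-management step with the same readers or software. It needs no extra assessor, visit or subject. The exact effort cannot be confirmed because the image system is redacted. Two limits remain and should be acknowledged in the plan: masking may be imperfect if a product leaves a trace, and bias from unblinded subjects taking the photos is not removed.
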